UFH	Unfractionated Heparin
WAIS	Wechsler Adult Intelligence Scale

Clarification of terms used:

Day 1 swab: Day 1 swab is defined as the swab taken before starting study drug. This could be on the same day as starting study drug.

Index case: The initial SARS-CoV-2 infected person who reached out for enrolment into the study. In the analysis, the index case is not analysed separately from the other household members. The index case does play a role in the randomisation by determining one of the randomisation strata. Some of the covariates included in multivariate models are also determined at the index case level.

Household contact: A household contact is any household member other than the index case.

Household member: This is a synonym for study participant, and means index cases and household contacts combined. For most analyses, we will include household members, by their SARS-CoV-2 status on day 1.

1. ADMINISTRATIVE INFORMATION

Protocol: Number: NCT05204550; Version: 10; date: 8 Feb 2024 ClinicalTrials.gov register Identifier: NCT05204550

1.1 Document version history

Version Date	Version	Author	Signature	Change Description	Reason/Comment
24 Feb 2025	1.0			Initial release.	Not applicable.

2. STUDY SYNOPSIS

The aim of this study is to address the question: Does early treatment of index case and early pre/post exposure prophylaxis of household members with intranasal heparin reduce transmission to household family contacts on Severe acute respiratory syndrome Coronavirus 2 (SARS-CoV-2) Polymerase chain reaction (PCR) assay by day 10, and subsequently reduce the burden of severe Coronavirus disease 2019 (COVID-19) as

measured by hospitalisation rates in exposed/infected people? A secondary outcome is whether intranasal heparin reduces the duration of transmissibility within the index case.

Multi-centre, prospective, cluster randomised, placebo-controlled two-arm superiority clinical trial.

Individual households with at least one person with PCR or RAT confirmed SARS-CoV-2 infection will be randomised so that all consenting people in that household receive intranasal heparin or placebo. Participants will receive intervention for 10 days and undergo 12 months of follow-up. The primary outcomes are achieved within 10 days. The majority of secondary outcomes related to primary COVID-19 infection are followed for 28 days from randomisation. The secondary outcomes related to "long COVID" are monitored at 6 and 12 months post randomisation.

The target sample size for the primary outcome is 1100 individuals. We planned to enroll 268 households and 1072 individuals.

The rate of subsequent PCR confirmed SARS-CoV-2 infections in exposed households will be measured to determine the effect of intranasal heparin on reducing transmission to close contacts.

The rate of symptom development in all participants will be used to determine effect of treatment in preventing symptomatic disease. The rate of hospitalisation of all participants will be measured to determine the effect of treatment on development of severe disease. The presence of clinical neurological long COVID symptoms will be assessed at 6 and 12 months to determine the effect of treatment on long COVID.

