2.2. Secondary objectives

1. To test the efficacy of intranasal heparin to reduce SARS-CoV-2 viral shedding over 10 days from day of positive swab (health professional collected swab day 3 and 5, and day 10)

Measure:

- 1.1. Total number of index cases and household contacts combined (nasopharyngeal swab positive on day 1), who remain swab positive on day 3
- 1.2. Total number of index cases and household contacts combined (nasopharyngeal swab positive on day 1), who remain swab positive on day 5
- 1.3. Total number of index cases and household contacts combined (nasopharyngeal swab positive on day 1), who remain swab positive on day 10
- 1.4. Time to swab negative based on health care provider collected nasal swab for household members (index cases and household contacts) who were swab positive on day 1 by PCR
- 1.5. Mean Ct values on days 3, 5 and 10
- 1.6. Lowest Ct value amongst household members who become positive during the first 10 days
- 2. To test the safety of intranasal heparin for treatment of adult and child outpatients with SARS-CoV-2 infection.

Measure:

2.1 The number of participants who discontinue treatment prior to day 10 from randomisation as a measure of treatment tolerability

2.2: Listing of adverse events and serious adverse events

3. To test whether intranasal heparin administration reduces symptomatic disease in index cases and household contacts.

Measure:

3.1 Number of household contacts (swab negative on day 1 of study) becoming symptomatic of COVID-19 in the next 28 days

Symptomatic COVID-19 is defined as:

- Fever or chills PLUS ≥1 respiratory symptom (sore throat, cough, shortness of breath);
- OR 2 respiratory symptoms (sore throat, cough, shortness of breath);
- OR 1 respiratory symptom (sore throat, cough, shortness of breath) PLUS ≥2 non-respiratory symptoms (chills, nausea, vomiting, diarrhea, headache, conjunctivitis, myalgia, arthralgia, loss of taste or smell, fatigue or general malaise).

3.2 Time to symptom resolution for index case and household contacts who were SARS-CoV-2 positive on day 1, during the study period as measured with daily symptom diary until day 28

- Common symptoms included in the symptom diary:
- Fever or chills
- Cough
- Shortness of breath or difficulty breathing
- Fatigue
- Muscle or body aches
- Headache
- New loss of taste or smell
- Sore throat
- Congestion or runny nose
- Nausea or vomiting
- Diarrheoa
- 4. To test the impact of intranasal heparin on peak severity of illness.

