6.3 Secondary outcome 3. Reduction of symptomatic disease

To test whether intranasal heparin administration reduces symptomatic disease in household members

Measure 3.1

Number of household contacts (swab negative on day 1 by PCR) becoming symptomatic of COVID-19 in next 28 days.

Symptomatic COVID-19 is defined as:

- Fever or chills PLUS ≥1 respiratory symptom (sore throat, cough, shortness of breath);
- OR 2 respiratory symptoms (sore throat, cough, shortness of breath);
- OR 1 respiratory symptom (sore throat, cough, shortness of breath) PLUS ≥2 non-respiratory symptoms (nausea or vomiting, diarrhea, headache, congestion or runny nose, sore throat, loss of taste or smell, myalgia, fatigue).

Symptoms are recorded as not present, mild, moderate or severe. A symptom will be regarded as being present if it is any of mild, moderate or severe.

Estimand

Population: Household contacts who test negative for SARS CoV-2 on day 1 by PCR

Treatment: Initially randomised intervention to unfractionated intranasal heparin 1400u each nostril (as heparin solution 5,000u/ml, 140microL/actuation, TWO actuations each nostril) THREE times daily via a plastic nasal inhalator device or saline control and any subsequent deviations to the per protocol use of the intervention over 10 days

Outcome: Becoming symptomatic of COVID-19 as defined above in the first 28 days.

Summary measure: Both relative (risk ratio) and absolute differences (risk difference) in proportions will be reported with 95% confidence intervals

Potential intercurrent events:

Index case in the household not taking study drug. This is defined as compliance <90% Participant (this household member) not taking study drug. This is defined as compliance <90% Either participant (this household member) or index case stop treatment due to adverse event Participant hospitalisation during first 10 days (removed from household) Participant received an anti-viral

Strategy for handling intercurrent event:

All intercurrent events will be handled through the treatment policy strategy, which means that the intercurrent events will be ignored.

The same analysis as described in Section 5.1 for the primary analysis will be done.

Measure 3.2

Days to symptom resolution for household members who were swab positive on day 1 by PCR, during the study period as measured with daily symptom diary until day 28.

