Common symptoms included in the symptom diary are: Fever or chills, cough, shortness of breath or difficulty breathing, fatigue, muscle or body aches, headache, new loss of taste or smell, sore throat, congestion or runny nose, nausea or vomiting, diarrhea. The symptoms are measured as not present, mild, moderate or severe. Symptom resolution is defined as a symptom improving by at least 2 categories from its first measurement (on Day 1) or being not present. For example, a symptom measured as severe on Day 1 would be resolved if it measured mild, all other symptoms would be resolved if it changed from moderate to not present or from mild to not present. Symptom resolution had to be maintained for 2 consecutive days.

Estimand

Population: Household members who test positive for SARS CoV-2 on day 1 by PCR

Treatment: Initially randomised intervention to unfractionated intranasal heparin 1400u each nostril (as heparin solution 5,000u/ml, 140microL/actuation, TWO actuations each nostril) THREE times daily via a plastic nasal inhalator device or saline control and any subsequent deviations to the per protocol use of the intervention over 10 days

Outcome: Days from randomisation to the first day with symptom resolution. Participants who still have symptoms on day 28 will be censored on day 28 and regarded as not having symptom resolution. Participants who had no symptoms at randomisation, will be regarded as having 0 days to symptom resolution. **Summary measure**: Median days to symptom resolution in each treatment arm. Hazard ratio. If all participants are symptom free at the end of follow-up, we will be able to estimate the difference in mean days to resolution of symptoms between the arms

Potential intercurrent events:

Index case in the household not taking study drug. This is defined as compliance <90% Participant (this household member) not taking study drug. This is defined as compliance <90% Either participant (this household member) or index case stop treatment due to adverse event Participant received an anti-viral

Strategy for handling intercurrent event:

All intercurrent events will be handled through the treatment policy strategy, which means that the intercurrent events will be ignored.

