Days to symptom resolution will be calculated from baseline to the first (of 2 consecutive days) day with symptom resolution (as defined above) for each of the symptoms individually. Participants who still have symptoms at the last time point will be censored at the time of last symptom checklist completed. Participants who are lost to follow-up will be censored at the last time a checklist was completed. The same analysis as described in Section 6.1 for endpoint 1.4 will be done.

In addition, an analysis for resolution of all symptoms will be done. This will be defined as the first day with all symptoms either mild or not present, maintained for 2 consecutive days. The analysis will be done in the same manner as for each individual symptom.

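### The synopsis promises an effect on symptom development in all participants, but the only incidence measure (3.1) covers day 1 PCR-negative contacts, and Measure 3.2 scores day 1-positive people who are still well as resolved at day 0

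*SAP*

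**What the plan says.** The synopsis (SAP Section 2) sets out how the effect on symptomatic disease will be judged: "The rate of symptom development in all participants will be used to determine effect of treatment in preventing symptomatic disease". Objective 3 in Section 2.2 is similarly broad: "To test whether intranasal heparin administration reduces symptomatic disease in index cases and household contacts".

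Two measures serve that objective.

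- **Measure 3.1** is the only one about becoming ill. Section 2.2 gives it as "3.1 Number of household contacts (swab negative on day 1 of study) becoming symptomatic of COVID-19 in the next 28 days", and Section 6.3 fixes the estimand as "Population: Household contacts who test negative for SARS CoV-2 on day 1 by PCR". The clarification of terms at the front of the SAP adds that "A household contact is any household member other than the index case".
- **Measure 3.2** covers household members who are PCR positive on day 1 and measures time to symptom resolution. Its outcome rule states: "Participants who had no symptoms at randomisation, will be regarded as having 0 days to symptom resolution". For the analysis of all symptoms together, resolution is reached early: "This will be defined as the first day with all symptoms either mild or not present, maintained for 2 consecutive days".

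Under objective 4 (Section 6.4), Measure 4.3 takes the highest daily symptom score to day 28, leaving out days 1 and 2, in everyone PCR positive on day 1. Measures 4.1 and 4.2 count hospitalisation by day 28, in day 1 positives and day 1-negative contacts respectively.

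**The concern.** The synopsis promises a comparison of symptom development across the whole trial population, and the analysis sections deliver it for one part only. The missing part is people already infected at entry but not yet ill. For them, preventing progression to illness is the early-treatment half of the trial's question; Measure 3.1 addresses the prophylaxis half.

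Measure 3.2 does not fill the gap, because it looks at resolution and not onset. Its 0-day rule also works in the wrong direction. A participant who is well at randomisation and develops symptoms on day 4 gets the shortest possible resolution time, so progression is recorded as immediate success. Two participants with opposite courses, one who stays well and one who becomes ill, receive the same value.

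A report that followed the SAP could therefore describe an effect on symptomatic disease in index cases and contacts while giving no incidence estimate for anyone PCR positive on day 1.

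**Working it through.** **Step 1: follow one participant through the measures.** Take someone PCR positive on day 1, aged 5 or over, with no symptoms at randomisation, who falls ill between days 3 and 28.

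| Measure | Population | What happens to this person |
|---|---|---|
| 3.1 becoming symptomatic | day 1-negative contacts | not included |
| 3.2 time to resolution | day 1 positives | included, scored 0 days; later illness not seen |
| 4.3 peak score, days 3-28 | day 1 positives | included; illness seen as a higher score |
| 4.1 hospitalisation | day 1 positives | event only if admitted |

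The later illness is thus registered as severity, and as an admission if there is one. It is never registered as a new case of symptomatic COVID-19.

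**Step 2: compare with hospitalisation.** The synopsis makes the same all-participant promise for hospitalisation. There the SAP keeps it with two strata, 4.1 (day 1 positive) and 4.2 (day 1 negative). For symptom development only the negative stratum exists.

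**Step 3: the all-symptom version of 3.2.** It requires every symptom to be mild or absent on two consecutive days. Someone with no or only mild symptoms on days 1 and 2 meets this at once, whatever happens afterwards. The difficulty therefore reaches beyond those with no symptoms at all.

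**Step 4: possible size.** The plan's own figures come first: 120/0.9 = 133.3, so 134 households per arm; 2 x 134 = 268 households; 268 x 4 = 1072 people, of whom 268 are index cases and 268 x 3 = 804 are contacts. The SAP gives no day 1 positivity among contacts and no share of positives still without symptomatic disease, so both are assumed here:

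- c = share of contacts PCR positive on day 1, 10% to 40%
- s = share of day 1 positives not meeting the symptomatic definition on day 1, 10% to 30%
- all index cases counted as PCR positive on day 1

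Negatives N = 804(1 - c). Positives P = 268 + 804c. People outside 3.1 but still at risk x = sP.

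| c | N | P | x at s = 10% | x at s = 30% |
|---|---|---|---|---|
| 10% | 723.6 | 348.4 | 35 | 105 |
| 20% | 643.2 | 428.8 | 43 | 129 |
| 40% | 482.4 | 589.6 | 59 | 177 |

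The share of all incident events that this group would carry depends on its risk. With equal risk in both groups it is x/(x + N): 34.8/758.4 = 5% at the low corner and 176.9/659.3 = 27% at the high corner. If 60% of x and 40% of N become symptomatic (also assumed), it is 0.6x/(0.6x + 0.4N): 20.9/(20.9 + 289.4) = 7% and 106.1/(106.1 + 193.0) = 35%.

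These counts describe people who do not meet the symptomatic definition, which needs a combination of symptoms. They are not the number affected by the 0-day rule: someone with only a cough fails the definition but is not symptom-free. That smaller group cannot be sized from the SAP.

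**The case against.** The strongest reply is that objective 3 is not restricted to incidence. Measures 3.1 and 3.2 together address day 1 negatives and day 1 positives, and Sections 2.2 and 6.3 agree on the population of 3.1. On that reading the only mismatch is one general sentence in the synopsis, which could simply be narrowed. Much of this stands: objective 3 is partly met, and the direct conflict is with the synopsis sentence. It does not rescue 3.2, whose 0-day rule hides the onset of illness in the very group it is meant to cover.

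A second reply is that an added endpoint, in a plan that describes randomisation in the past tense and makes no multiplicity adjustment (Section 3.5), has a cost. That also stands, and is why the analysis should be labelled as added.

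Two stronger readings should be resisted.

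- A reader might infer that illness arising in day 1 positives is counted nowhere. It is not so: Measure 4.3 includes everyone PCR positive on day 1 without any baseline-symptom condition and compares arms on the peak score, and 4.1 captures admissions. Neither replaces incidence, because 4.3 is a mean difference in a summed score that mixes people already ill with people newly ill and does not apply the symptomatic definition.
- A reader might infer that 3.1 is an undeclared narrowing of the protocol because Section 2.8 does not list it. Section 2.8 concerns departures from the protocol, not from the synopsis, and the SAP alone cannot show whether the protocol was broader.

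**Conclusion.** The point holds in a limited form. The synopsis promises more than Measure 3.1 delivers. No measure gives the incidence of symptomatic COVID-19 in day 1-positive participants who are not yet ill, and Measure 3.2 scores the symptom-free among them as resolved at day 0 whatever follows. These conclusions rest on the text alone and need no assumption.

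The size is uncertain. The range of about 35 to 177 people, against 482 to 724 in Measure 3.1, rests wholly on assumed shares, and its upper end needs both shares at their extremes. It shows that the group need not be negligible, and no more than that.

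This is a secondary outcome; the primary analysis is not affected. The change is worth making because it is cheap and supplies a comparison that the SAP says it will use.

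**What to change.** 1. **Section 6.3 and Table 13.** Add, labelled as an added secondary analysis, incident symptomatic COVID-19 by day 28 in day 1-positive participants who do not meet the Section 6.3 definition on day 1. Use the Section 5.1 models and show the result beside the unchanged Measure 3.1, as 4.1 and 4.2 do for hospitalisation. A pooled estimate adjusted for day 1 PCR status is optional.
2. **Measure 3.2.** Drop the 0-day assignment. Restrict each time-to-resolution analysis to participants who have the symptom at baseline. For the all-symptom analysis, the matching restriction is to those with at least one symptom above mild at baseline. Baseline is measured before study drug is dispensed (Section 3.3), so the restriction does not condition on anything that treatment can change.
3. **Section 2.** Reword the synopsis sentence so that it refers to participants without symptomatic COVID-19 on day 1.

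The cost is SAP wording, one further model and one block of rows in Table 13. The daily diary to day 28 is already used for day 1 positives in 3.2 and 4.3, so no new data are needed. The downside is one more secondary comparison without multiplicity adjustment, in a stratum that may be small and whose size the SAP does not give. Models with the full covariate set may not converge there, in which case the fallbacks in Sections 3.9 and 5.1 apply.

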2.1. Primary objective

To test the efficacy of early treatment and post exposure prophylaxis to reduce transmission to household family contacts on SARS-CoV-2 PCR assay by day 10.

Measure: Number of household contacts (swab negative on day 1) testing positive for SARS-CoV-2 by PCR on either of three routine nasopharyngeal swabs on day 3, 5 and 10 after enrolment or on clinically driven swab in the first 10 days. Day 1 swab is defined as the swab taken before starting study drug. This could be on the same day as starting study drug.

2.2. Secondary objectives

1. To test the efficacy of intranasal heparin to reduce SARS-CoV-2 viral shedding over 10 days from day of positive swab (health professional collected swab day 3 and 5, and day 10)

Measure:

- 1.1. Total number of index cases and household contacts combined (nasopharyngeal swab positive on day 1), who remain swab positive on day 3
- 1.2. Total number of index cases and household contacts combined (nasopharyngeal swab positive on day 1), who remain swab positive on day 5
- 1.3. Total number of index cases and household contacts combined (nasopharyngeal swab positive on day 1), who remain swab positive on day 10
- 1.4. Time to swab negative based on health care provider collected nasal swab for household members (index cases and household contacts) who were swab positive on day 1 by PCR
- 1.5. Mean Ct values on days 3, 5 and 10
- 1.6. Lowest Ct value amongst household members who become positive during the first 10 days
- 2. To test the safety of intranasal heparin for treatment of adult and child outpatients with SARS-CoV-2 infection.

Measure:

2.1 The number of participants who discontinue treatment prior to day 10 from randomisation as a measure of treatment tolerability

2.2: Listing of adverse events and serious adverse events

3. To test whether intranasal heparin administration reduces symptomatic disease in index cases and household contacts.

Measure:

3.1 Number of household contacts (swab negative on day 1 of study) becoming symptomatic of COVID-19 in the next 28 days

Symptomatic COVID-19 is defined as:

- Fever or chills PLUS ≥1 respiratory symptom (sore throat, cough, shortness of breath);
- OR 2 respiratory symptoms (sore throat, cough, shortness of breath);
- OR 1 respiratory symptom (sore throat, cough, shortness of breath) PLUS ≥2 non-respiratory symptoms (chills, nausea, vomiting, diarrhea, headache, conjunctivitis, myalgia, arthralgia, loss of taste or smell, fatigue or general malaise).

3.2 Time to symptom resolution for index case and household contacts who were SARS-CoV-2 positive on day 1, during the study period as measured with daily symptom diary until day 28

- Common symptoms included in the symptom diary:
- Fever or chills
- Cough
- Shortness of breath or difficulty breathing
- Fatigue
- Muscle or body aches
- Headache
- New loss of taste or smell
- Sore throat
- Congestion or runny nose
- Nausea or vomiting
- Diarrheoa
- 4. To test the impact of intranasal heparin on peak severity of illness.

Measure:

- 4.1. Number of index cases and household contacts swab positive on day 1, hospitalised with COVID-19 by day 28 from randomisation
- 4.2. Number of household contacts swab negative on day 1, hospitalised with COVID-19 by day 28 from randomisation
- 4.3 Maximum severity score of participants (index case and household contacts swab positive) during the study period as recorded by daily symptom diary up to day 28.

A COVID-19 Composite Subjective Symptom Severity Score (CCSSSS) will be generated using the 11 common symptoms for COVID-19 infection listed at the Centers for Disease Control and Prevention (CDC) website and a self-rated symptom severity assessment generated for each symptom on a daily basis using a Likert scale for each symptom (Scale 0-3: not present, mild, moderate, severe).

Common symptoms:

- Fever or chills
- Cough
- Shortness of breath or difficulty breathing
- Fatigue
- Muscle or body aches
- Headache
- New loss of taste or smell
- Sore throat
- Congestion or runny nose
- Nausea or vomiting

• Diarrhea

Each symptom will be assigned a score of 0 if not present, 1 if mild, 2 if moderate and 3 if severe. These scores for each symptom will be added together to get the CCSSSS for each day.

5. To assess the impact of intranasal heparin on long COVID neurological symptoms.

Measure:

5.1 Number of participants with clinical symptoms of neurological long COVID at 6 months post randomisation.

The following symptoms were rated via telehealth or in person using a self-rated symptom assessment using a Likert scale (0-3: absent, mild, moderate, severe) for each symptom:

- Fatigue
- Malaise
- Daytime tiredness
- Impaired concentration
- Brain fog
- Sleep disturbance
- Forgetfulness
- Confusion
- Headache
- Dizziness
- Nausea
- Hypo/anosmia
- Hypo/ageusia
- Impaired walking
- Tingling feet or hands
- Burning feet or hands
- Numb feet or hands
- Impaired fine motor skills
- Muscle pain
- Epilepsy
- Anxiety
- Depression

For participants over 16 years of age, cognition and mood were assessed using the harmonised procedures developed by the Neuro-COVID Neuropsychology International Task force. Included measures were:

- Cognitive screening using Telephone Montreal Cognitive Assessment (T-MoCA)
- Subjective cognitive complaints using Patient's Assessment of Own Functioning Inventory (PAOFI)
- Attention/working memory using the Wechsler Adult Intelligence Scale (WAIS) digit span
- Mood using the Depression, Anxiety and Stress Scales (DASS)
- 5.2 Number of participants with clinical symptoms of neurological long COVID at 12 months post participation in trial.

